MAPS is a holistic, dynamic approach to facilitating behavior change that utilizes a combined motivational enhancement and social cognitive approach based on motivational interviewing (MI)^{18,19} and social cognitive theory.²⁰⁻²² MAPS is designed for all individuals regardless of their readiness to change, and specifically targets motivation and intrinsic motives for change, social cognitive constructs (e.g., agency/self-efficacy), and other factors of key relevance to cervical cancer survivors (e.g., stressors, anxiety, depression, family conflicts, finances, fear of cancer recurrence). Because MAPS revolves around a Wellness Program that addresses numerous barriers and concerns that are prevalent among cervical cancer survivors, we believe it is particularly appropriate for treating this population. Furthermore, the delivery of this intervention via telephone offers a less resource intensive modality while also minimizing participant burden.

The specific aims are to:

1. Compare the efficacy of a MAPS approach to promoting and facilitating smoking cessation to ST among cervical cancer survivors.
2. Assess the effects of MAPS on hypothesized treatment mechanisms (motivation, agency, and stress/negative affect) and the role of those mechanisms in mediating MAPS effects on abstinence.
3. Compare the cost-effectiveness of MAPS and ST.

SIGNIFICANCE

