Stress/Negative Affect. Stress and negative affect, measured in many different ways, predict cessation outcomes. Affective predictors include affective responses to smoking-related acute events, individual differences in affective vulnerability, depressive symptoms, and the magnitude and trajectory of stress/negative affect over time.^{19,81,87,93-97} In addition to the stress/negative affect engendered by cessation, life stressors such as those experienced by cervical cancer survivors, have been shown to have adverse effects over time on motivation, self-efficacy, and abstinence.^{98,99} Further, social cognitive theory posits that weak motivation for abstinence can increase stress/negative affect, particularly during high-risk situations.²¹ Thus, MAPS is hypothesized to reduce stress/negative affect via its impact on decreasing ambivalence and increasing motivation, through the application of coping skills training and problem-solving, and through utilization of a holistic approach in which other life concerns and stressors are addressed.

APPROACH

Project Design and Procedures. Participants will be women with a diagnosis of cervical cancer or high grade cervical dysplasia who report smoking any cigarettes within the past 30 days, recruited through the Stephenson Cancer Center or OU Physicians at the University of Oklahoma Health Sciences Center, via the ClinicalTrials.gov website, by responding to recruitment flyers and internet advertisements (e.g., flyers in clinics, Facebook), and through referrals from healthcare providers. Participants will be followed for a period of 18 months, and randomly assigned to one of two groups: 1) Standard Treatment [ST], or 2) Motivation and Problem Solving [MAPS]. ST will consist of a mailed packet of materials including a letter referring smokers to the Oklahoma Tobacco Helpline, Florida Quitline or to the national quitline number ([name]) for participants residing in other states, free nicotine replacement therapy when they are ready to quit, and standard self-help materials. ST will be mailed a total of 3 times to participants with completed assessments (at Baseline, 6 and 12 months). MAPS will consist of ST plus up to 6 proactive phone counseling sessions delivered over a 12-month period. The timing of counseling sessions in MAPS is flexible and determined jointly by the participant and the counselor.

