Assessment calls will occur at Baseline and at 3, 6, 12, and 18 months after Baseline. The primary outcomes are abstinence from tobacco at the 18-month follow-up and abstinence across all follow-ups. Secondary outcomes are smoking quit attempts, cigarettes per day, use of the quitline, and cost-effectiveness. Participants will be scheduled to complete a baseline assessment call within one week. Following the baseline assessment, participants will be randomly assigned to ST or MAPS. Participants will schedule their first counseling call at that time (see Table 1).

Recruitment. Participants will be women with a diagnosis of cervical cancer or high grade cervical dysplasia who report smoking any cigarettes within the past 30 days, recruited through the Stephenson Cancer Center or OU Physicians at the University of Oklahoma Health Sciences Center, via the ClinicalTrials.gov website, by responding to recruitment flyers and internet advertisements (e.g., flyers in clinics, Facebook), and through referrals from healthcare providers.

Participant Eligibility. Inclusion criteria: ≥ 18 ; current smoker with a history of at least 100 lifetime cigarettes and a self-report of smoking within the last 30 days; history of cervical cancer or high grade cervical dysplasia (we have defined survivorship as beginning at the time of cancer diagnosis, consistent with the NCI definition); has a working cell phone; valid home address; speaks English, Spanish or both languages. Exclusion criteria: current use of tobacco cessation medications; self-report of being pregnant or lactating; or, another household member enrolled in the study; or contraindication of nicotine patch use unless under the supervision of a physician as advised by project staff.

Table 1. Schedule of Study Procedures and Assessments	Screening	Baseline	Month 3	Month 6	Month 12	Month 18
Inclusion/Exclusion Criteria	X	X				
Compensation		\$60	\$60	\$60	\$60	\$60
TREATMENT PROCEDURES						
Standard Treatment (ST)	Delivered at Baseline, and Months 6 and 12					
Motivation And Problem Solving (MAPS)	ST plus up to 6 MAPS Counseling Calls delivered over 12 months					
DEMOGRAPHICS, MENTAL HEALTH						
Demographics and Smoking History		X				
Cancer stage at diagnosis, time since diagnosis, current stage, treatment status	X					
Subjective Social Status		X	X	X	X	X
Fear of Cancer Recurrence Inventory (FCRI)	X	X	X	X	X	X
MOTIVATION						
Contemplation Ladder		X	X	X	X	X

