Because the primary and secondary outcomes and mechanisms include repeated measurements that are correlated within subjects, our data analytic approach will also utilize generalized linear mixed model regression (GLMM)^{107,108} to analyze the effects of MAPS across the 3, 6, 12, and 18 month timepoints. For abstinence, we will assume a logit link and binomial variance function for the GLMM, and parameterize them with blocking on individual nested within treatment conditions. Treatment and time will be included, as well as their interaction, with adjustment for relevant covariates. The effects of interactions between treatment and specific covariates will also be examined. Similarly analyses will also be conducted to assess the MAPS effects on quit attempt and use of the quitline (both binary). To assess MAPS effects on continuous measures such as cigarettes per day and mechanisms, the GLMM analysis will be replaced by linear mixed model (LMM) analysis (i.e., a special case of the GLMM). Similarly, the logistic regression analysis for the 18-month assessment will be replaced by multiple linear regression. Normalizing transformations for continuous measures (such as cigarettes per day) will be applied as appropriate. Alternatively, Poisson GLMM or Poisson regression could be used to analyze the effect of MAPS on cigarettes per day. In addition to examining the effects of treatment on primary and secondary outcomes and mechanisms, we will also assess the mediation (indirect) effects of treatment on abstinence through the mechanisms (motivation, agency, stress/negative affect) using single and/or multiple mediator models.¹⁰⁹ With the primary outcome being abstinence at the 18-month assessment, potential mediators will be mechanisms measured at the previous time points (i.e., 3, 6, and 12 months), one at a time. A recommended approach to estimating and/or testing for the indirect effects for a binary outcome variable is via coefficient standardization in the *b* path (e.g., logistic regression), as appropriate, and bootstrapping.¹⁰⁹⁻¹¹¹ Appropriate covariates including mediators measured as baseline will be

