adjusted for in the *a* and *b*-path analyses. Mediators in the final mediator model will be selected using a backward selection approach.¹¹² We will also compute and compare proportions of mediated effects along with their standard errors across the single and multiple mediator models, as well as across time points where the mediators are measured.¹¹³ A larger proportion of the mediated effect in general suggests a larger mediation effect. Additional mediation analysis for repeated measures abstinence analyses will be conducted using a similar approach with both *a* and *b* paths involving repeated measures analysis, as applicable.¹¹³

Missing Data and Dropouts. It is anticipated that some individuals will drop out or be lost to follow-up, as is typical in smoking cessation treatment studies. Our primary analysis for examining abstinence at 18 months will utilize an intent-to-treat approach by coding missing abstinence data as smoking. However, we will also conduct sensitivity analyses by examining alternative approaches for handling missing data, including multiple imputation (under a missing at random assumption),^{114,115} and selection models (under an assumption of non-ignorable missingness, or missing not at random).^{114,116-118} In the multiple imputation approach, we will conduct analyses to examine whether participants who drop out of the study differ from those who do not, and include those covariates in our multiple imputation models, to mitigate the potential impact of non-ignorable missingness. Regardless of the approach used to handle missing data, it is unlikely that serious biases in estimation or considerable loss of efficiency in inference will result when the proportion of missing data low (e.g., not more than 10%; even more so when the missing data proportions are similar in MAPS and ST).

Overall, robust results based on both the primary and sensitivity analyses will strengthen our study findings.

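### The Aim 2 mediation models do not account for women who had already quit when the mediator was measured, so quitting itself can create or mask an apparent indirect effect of MAPS

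*Combined protocol and SAP*

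**What the plan says.** Specific Aim 2 is to assess the effects of MAPS on motivation, agency and stress/negative affect, and "the role of those mechanisms in mediating MAPS effects on abstinence". Under Statistical Considerations, Data Analysis Approach, the plan estimates "mediation (indirect) effects of treatment on abstinence through the mechanisms (motivation, agency, stress/negative affect) using single and/or multiple mediator models". With 18-month abstinence as the outcome, "potential mediators will be mechanisms measured at the previous time points (i.e., 3, 6, and 12 months), one at a time". Indirect effects are tested by bootstrapping, and proportions mediated are to be compared across models and time points.

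On adjustment the text reads "Appropriate covariates including mediators measured as baseline will be" and continues "adjusted for in the *a* and *b*-path analyses". No other covariate is named for these paths. The plan adds: "Additional mediation analysis for repeated measures abstinence analyses will be conducted using a similar approach". It states no lag between mediator and outcome there.

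Three other places bear on the point:

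- **Participant Eligibility** requires a "current smoker with a history of at least 100 lifetime cigarettes and a self-report of smoking within the last 30 days", so quitting happens during follow-up.
- **Table 1** collects smoking status and all the mechanism scales at months 3, 6, 12 and 18.
- **Significance, Stress/Negative Affect** opens a sentence with "In addition to the stress/negative affect engendered by cessation", so the protocol itself says that quitting moves one of the mediators.

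**The concern.** Measuring the mediator at month 3 and the outcome at month 18 looks like correct temporal order, but the outcome state can begin before month 3. A woman who quits in month 1 may report a different level of self-efficacy, motivation or stress at month 3 because she has quit. She is also more likely than others to be abstinent at month 18. MAPS is expected to increase quitting, so early quitting is affected by treatment, moves the mediator and predicts the outcome. Adjusting for the baseline mediator cannot remove that.

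The direction depends on the mechanism. If quitting improves the score, an inert mechanism looks like a mediator in the hypothesised direction. If quitting raises stress, as the protocol suggests, the association induced by quitting runs against the hypothesised one. Both paths of a real stress-reducing mechanism are then pulled toward zero, and mediation can be missed.

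At stake is what Aim 2 can conclude: whether MAPS worked through, say, self-efficacy, or whether women who quit then felt more confident.

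**Working it through.** **The plan's own figure.** The Power section gives 80% power for a 0.376 SD difference in a mechanism with 112 per group (25% attrition: 0.75 × 150 = 112.5). Check: 0.376 × √(112/2) = 2.814; 2.814 − 1.960 = 0.854; Φ(0.854) = 80.3% (80.0% with the noncentral t). It reproduces. It describes power for a treatment effect on a mechanism and says nothing about the bias considered here.

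**Simulation of the planned model with an inert mechanism.**

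- From the documents: two-sided 0.05; n = 224 (2 × 112); 10% vs 21.9% abstinent. The documents give these rates for month 18; using them at the mediator visit is an assumption.
- Assumed: 60% of women abstinent at the visit and 6% of the others are abstinent at month 18; mediator correlated 0.5 with its baseline; quitting shifts the mediator by d SD; the mediator has no effect on abstinence.
- a path: linear regression of mediator on arm and baseline mediator.
- b path: logistic regression of 18-month abstinence on arm, baseline mediator and mediator.
- Companion b path: the same plus abstinence at the visit.
- Indirect effect: both paths significant, standing in for the planned bootstrap test.

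The implied 18-month rates are 0.10 × 0.60 + 0.90 × 0.06 = 11.4% (ST) and 0.219 × 0.60 + 0.781 × 0.06 = 17.8% (MAPS).

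Share of 1,500 simulated trials that are significant:

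| Shift d | a path | b path | Both | Companion b | Both, companion |
|---|---|---|---|---|---|
| 0 | 5.5% | 4.9% | 0.3% | 4.9% | 0.3% |
| 0.5 | 8.9% | 39.3% | 3.3% | 5.6% | 0.4% |
| 0.8 | 12.3% | 75.1% | 9.6% | 4.9% | 0.9% |
| 1.0 | 16.3% | 88.5% | 14.3% | 5.3% | 1.1% |

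With 8% instead of 6% abstinent at month 18 among the others, and shifts of 0.5, 0.8 and 1.2 SD, the b path is falsely significant in 32%, 64% and 91% of trials and both paths in 3%, 8% and 18%. The companion brings the latter to 1% or less.

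**Why the indirect effect is much rarer than the b path.** The a path created by quitting is d × (0.219 − 0.10): 0.060 SD at d = 0.5 and 0.143 SD at d = 1.2, well below the 0.376 SD that the trial can detect. The joint rate is roughly the product of the two path rates: 8.9% × 39.3% = 3.5%, against 3.3% simulated.

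**Larger samples do not help.** At n = 300 the b path is falsely significant in 49%, 84% and 95% of trials (d = 0.5, 0.8, 1.0) and both paths in 5%, 13% and 19%. The large-sample proportion mediated for the inert mechanism is about 4%, 10% and 14%.

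**What the companion model does to a real mediator.** Assume that MAPS shifts the mechanism by 0.4 to 0.6 SD and that the mechanism drives quitting by the visit (log odds 0.7 to 1.3 per SD). Assume also that 60% vs 8% are then abstinent at month 18, with no other route. The planned model detects mediation in 20% to 70% of trials and the companion in 4% to 5%; one setting inside that range gives 52% against 5%. With an added direct effect of log odds 0.4 per SD, detection falls from 67% to 98% under the planned model to 28% to 33% under the companion.

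**Restricting to women still smoking.** With 112 per group, 112 × 0.90 + 112 × 0.781 ≈ 188 women remain at the visit. At 8% that is about 15 events.

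**The case against.** Several points on the other side stand.

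- The b path alone is not a test of mediation, so its 30% to 90% must not be read as the rate of falsely declared mediators. For a 0.5 SD shift the false indirect effect stays below 5%.
- The protocol's theory is that mechanisms lead to quitting and then to maintained abstinence. Abstinence at the visit may therefore be part of the pathway, and conditioning on it can erase true mediation. A rule that accepts a mediator only if it survives conditioning would reject mechanisms that work as MAPS intends.
- The covariate wording is open, so adjusting for earlier abstinence is permitted. It is not required, and an analyst following the text could leave it out.
- A reader might infer that follow-up smoking status goes unused. It does not: abstinence at 3, 6 and 12 months enters the mixed model, and a repeated-measures mediation analysis is planned. Neither settles whether the mechanism or the quitting came first.
- The Power section calls Aim 2 quasi-exploratory and leaves tests of specified mediational models to future studies. That lowers the stakes. But the caveat accepts inflated type 1 error from multiple tests, which is a matter of chance; this is a systematic bias that persists as the sample grows.

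**Conclusion.** The concern holds in limited form. The mediation models as written cannot distinguish a mechanism that leads to quitting from one that changes because of quitting, and the plan requires no analysis that addresses this. Under the assumed inputs, a false indirect effect appears in about 3% to 18% of trials per mechanism and visit, against about 0.5% or less when quitting does not shift the score. The plan examines three mechanisms at three visits, so the chance of at least one is higher; how much higher depends on correlations that the documents do not give. For stress/negative affect the likelier error is a missed mediator.

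The shift sizes, the persistence of abstinence, the baseline correlation and the abstinence rates at the visit are assumptions. Only the sample size, the significance level and the 10% and 21.9% rates (stated for month 18) come from the plan.

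A reader might infer that any positive Aim 2 result is uninterpretable, or that the trial's main result is compromised. Neither follows. The false indirect effect is modest at small shifts, and the primary 18-month comparison does not use the mediators.

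**What to change.** For each mediator model, pre-specify a companion b-path model that adds abstinence status at the mediator's assessment, using the same abstinence definition as the outcome. Report it beside the planned model with this reading:

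- Indirect effect in both models: the evidence for mediation is stronger.
- Indirect effect in the planned model only: the data cannot separate mediation through early quitting from an effect of quitting on the mechanism.

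Do not use the companion as a pass/fail rule. For the repeated-measures mediation, state that the mediator comes from an earlier visit than the outcome, and add abstinence at that earlier visit in the companion. For stress/negative affect, note that the bias may hide mediation.

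The cost is additional model fits on data already collected and two sentences on interpretation. The downside is that the companion loses most of its power for mechanisms that act through early quitting, so it cannot replace the planned model. Restriction to women still smoking should not replace it either: that is selection after randomisation and leaves few events.

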Power. Our power analysis is based primarily on the comparison of 18-month abstinence rates between MAPS and ST. Because an intent-to-treat approach will be used, power is calculated based on the full sample without attrition (N=300; 150 per group), given that individuals lost to follow-up will be treated as smoking). All power analyses assume a significance level of 0.05 and a two-sided test. Based on the *Guideline*,²⁰ we estimated that abstinence for ST would be approximately 10%. Using a chi-square test to examine the effect of treatment on abstinence at 18 months, a sample size of 300 (150 per group) will provide 80% power to detect an overall treatment effect that corresponds to abstinence rates of 10% and 21.9% in ST and MAPS respectively. Relative to examining abstinence over time, these calculations represent the worst case scenario. Table 2 presents detectable differences across a range of possible abstinence rates. Analyses conducted using GLMM will have greater power to detect the same average differences across time.

Table 2. Detectable differences in binary smoking outcomes with 80% power (abstinence, quit attempt)	
ST (n=150)	MAPS (n=150)
5.0%	14.60%
10.0%	21.90%
20.0%	34.40%
30.0%	45.70%
40.0%	56.20%

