Although the proposed mediation analyses for aim 2 are theoretically-grounded and hypothesis-driven (see Figure 1), they are quasi-exploratory in nature, and the sample size for this study was based on power to detect a significant difference for Aim 1. Nonetheless, power for the mediation analyses (Aim 2) has been calculated as follows. For the mechanism analyses (Aim 2), power is based on a conservative 25% attrition rate (N= 300; 112 per group). Because the mechanism variables are continuous, a sample size of 300 (112 per group at 18 months) will provide 80% power to detect an effect size of 0.376 standard deviation (SD) unit (difference in means between the ST and MAPS divided by common SD), using a two group t-test with a 0.05 two-sided significance level. Because we have excellent power to detect treatment effects on the primary outcome and mechanisms, as well as the effects of mechanisms on abstinence (with power generally greater using continuous predictors than binary predictors such as treatment group), we expect to have good power to detect mediation effects. We note, however, that the power calculated for analyses in Aim 2 should be considered in the context of inflated type 1 error due to multiple analyses and hypothesis tests (including the mediation analyses) being performed for this aim. We feel that this inflated type 1 error is acceptable given the quasi-exploratory nature of this aim. Nevertheless, future studies focusing on testing specified mediational models should be sufficiently powered using approaches of Fritz and MacKinnon¹¹⁹ or Thoemmes et al.¹²⁰, as appropriate.

Cost Effectiveness

Methods overview. Cost-effectiveness analyses (CEA) will compare the two interventions: ST and MAPS. The conventional CEA summarizes study findings in terms of the incremental cost-effectiveness ratio (ICER).^{121,122} The ICER, calculated as the difference in mean costs between the new and standard treatment divided by the difference in mean effectiveness between the new and standard treatment, estimates the additional resource consumption needed to achieve an increase in an additional unit of effectiveness. The ICER is then compared with a commonly cited or published threshold value associated with an intervention already found to be cost-effective to determine whether a new intervention is cost-effective.

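### Backward selection of mediators for the final model overstates those that survive, and the proportion mediated is too unstable to compare across models or time points

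*Combined protocol and SAP*

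**What the plan says.** Under Statistical Considerations, Data Analysis Approach, mediation of 18-month abstinence is to be examined in single and/or multiple mediator models. The mechanisms are motivation, agency and stress/negative affect, taken at 3, 6 and 12 months in turn, and the indirect effects use a standardized logistic b path and bootstrapping. For the final model: "Mediators in the final mediator model will be selected using a backward selection approach". The plan lists no candidates and gives no retention threshold, and it does not say whether the selection is repeated in each bootstrap resample. Table 1 lists nine instruments under the three mechanism headings.

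The same section then compares proportions mediated, with standard errors, between single and multiple models and between time points. The reading given is: "A larger proportion of the mediated effect in general suggests a larger mediation effect".

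The Power section sets Aim 2 at 112 per group and calls it quasi-exploratory. On multiple testing it says: "We feel that this inflated type 1 error is acceptable given the quasi-exploratory nature of this aim".

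**The concern.** Selection and estimation use the same data. A mediator stays in the final model only if its estimated b path is large relative to its standard error, so the estimates that get reported are the ones that came out high. That is bias in the estimate, a different problem from the false-positive rate that the Power section accepts.

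The proportion mediated adds a second difficulty. It divides a small indirect effect by a total effect that is itself imprecisely estimated. When the denominator can come close to zero, the ratio swings widely and its standard error is a poor guide.

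At stake is the Aim 2 report: which mechanisms are said to explain the MAPS effect, how strongly, and at which time point.

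**Working it through.** **Inputs from the Power section.** Test level: "All power analyses assume a significance level of 0.05 and a two-sided test". Aim 1: "power is calculated based on the full sample without attrition (N=300; 150 per group", with "abstinence rates of 10% and 21.9% in ST and MAPS respectively". Aim 2: "power is based on a conservative 25% attrition rate (N= 300; 112 per group", which "will provide 80% power to detect an effect size of 0.376 standard deviation (SD) unit".

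**The plan's own figures reproduce.**
- Aim 2: 0.376 × √(112/2) = 2.814, and Φ(2.814 − 1.96) = 0.803. The noncentral t gives 0.800.
- Aim 1: 150 per group, 10% v 21.9%, gives power 0.807.

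**Expected abstainers.** 150 × (0.10 + 0.219) = 47.9. With 112 per group, 112 × 0.319 = 35.7. The second figure assumes that the planned rates apply to the women with mechanism data; the plausible range is 36 to 48.

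**Why selection inflates the estimate (approximation for one mediator, SD 1).**
- Information for b is about 112 × 0.10 × 0.90 + 112 × 0.219 × 0.781 = 10.08 + 19.16 = 29.24.
- SE = 1/√29.24 = 0.185. Correlated mediators in the same model make it larger.
- Retention at p<0.05 needs an estimate above 1.96 × 0.185 = 0.36. For a true b of 0.25, that is at least 0.36/0.25 = 1.4 times truth.
- Mean estimate given retention = b + SE × φ(k)/(1 − Φ(k)), with k = 1.96 − b/SE. For b = 0.25, k = 0.61 and the mean is 0.476, or 1.9 times truth. For b = 0.4, k = −0.20 and the mean is 0.525, or 1.3 times. For b = 0.6, k = −1.28 and the mean is 0.636, or 1.06 times.

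**Simulation of the whole step.** Settings not in the documents are assumptions: 3 or 9 candidates, mediator correlation, true b, and the retention cut-off. The a path is 0.376 SD and abstinence is 10% v 21.9%. The rows below use nine candidates, correlation 0.4 and 112 per group.

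| True b (true mediators) | Cut-off | Retained | b, estimate/truth, selected | Coverage of b, selected | Coverage of indirect effect, selected | b, estimate/truth, no selection |
|---|---|---|---|---|---|---|
| 0.25 (3) | 0.05 | 27% | 2.43 | 0.70 | 0.84 | 1.07 |
| 0.25 (3) | 0.10 | 36% | 2.16 | 0.84 | 0.90 | 1.06 |
| 0.4 (3) | 0.05 | 48% | 1.70 | 0.88 | 0.93 | 1.07 |
| 0.4 (3) | 0.10 | 57% | 1.58 | 0.92 | 0.95 | 1.09 |
| 0.6 (2) | 0.05 | 75% | 1.26 | 0.95 | 0.96 | 1.08 |
| 0.6 (2) | 0.10 | 82% | 1.22 | 0.95 | 0.96 | 1.10 |

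With three candidates, two true at b = 0.4 and cut-off 0.10, the ratio is 1.45 against 1.05 without selection. A separate set of runs over 3 and 9 candidates gave 1.1 to 2.2 times truth, with coverage 0.83 to 0.92 at b = 0.25. Without selection it gave 1.01 to 1.11 times, with coverage of about 0.93 to 0.96. The verdict uses this more moderate range; the first table row lies beyond it.

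**Denominator of the proportion mediated.**
- Total effect = ln(0.219/0.781) − ln(0.10/0.90) = 0.926.
- SE = √[1/(n × 0.10) + 1/(n × 0.90) + 1/(n × 0.219) + 1/(n × 0.781)] = 0.336 for n = 150 and 0.389 for n = 112.
- Ratio to SE: 0.926/0.336 = 2.8 and 0.926/0.389 = 2.4.
- With n = 112 the 95% range of the total effect is 0.926 ± 1.96 × 0.389, or 0.16 to 1.69. Hold the indirect effect at 0.376 × 0.4 = 0.150. The proportion is 0.150/0.926 = 0.16 at the planned effect, but runs from 0.150/1.69 = 0.09 to 0.150/0.16 = 0.94 over that range.
- Simulated with numerator and denominator both varying, a true proportion of about 0.18 has a central 95% range of about 0.01 to 0.75 (112 per group) or 0.03 to 0.57 (150). If abstinence were 10% v 16% (assumed), the range is about −2 to +3.

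**The case against.** The strongest reply is that the aim is labelled quasi-exploratory, its multiplicity is disclosed, and testing of specified mediation models is left to future studies. Much of this stands, and it rules out several stronger readings.

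- **False retention.** A reader might point to irrelevant mediators being kept: 38–40% of trials with nine null candidates at p<0.05, and 60–63% at p<0.10. That is almost entirely multiplicity: 1 − 0.95⁹ = 37% and 1 − 0.90⁹ = 61%. In one run selection kept a null in 38.7% of trials, and the unselected model had a significant null in 39.0%. The plan accepts this, so it is not an argument against selection.
- **Intervals that never cover zero.** A null b path kept because p<0.05 has a 95% interval that excludes zero by construction. This shows nothing about the planned bootstrap of the indirect effect.
- **Intervals that certainly ignore selection.** The plan is silent on this. It cites a source for backward selection that is not available here, and the single-mediator models need no selection.
- **A ranking that is mostly noise.** The stated comparison is across models and time points, hedged and given with standard errors; a ranking of mechanisms is only implied. Among three time points the top one was right in 61–66% of simulated trials for true proportions of 0.14/0.19/0.24. It was right in 83–88% for about 0.08/0.15/0.26, and only at chance when the proportions were equal.

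The reply also limits the remedy. Nine mediators, their nine baselines, treatment, 8 to 12 covariate terms and an intercept make 28 to 32 parameters on about 36 abstainers. Such a model is itself overfitted (b 1.24 to 1.29 times truth, coverage about 0.92).

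What the reply does not meet is the bias in the estimates. Accepting more false positives is not accepting that true mediators are reported too large, and the same section also expects good power for mediation.

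**Conclusion.** The point holds in a limited form. In the final multiple-mediator model, a true mediator that survives backward selection is overstated by about 1.1 to 2.2 times in its b path. The upper end belongs to weak mediators (b = 0.25 per SD), where coverage falls to about 0.83–0.92; at b = 0.6 the effect is small. These figures rest on assumed effects, correlations, 3 or 9 candidates and retention at p<0.05 or 0.10, because the plan states no candidate list or rule, and on selection not being repeated in the bootstrap.

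The instability of the proportion mediated needs fewer assumptions: at the planned rates its denominator is about 2.4 to 2.8 standard errors from zero, and closer if the effect is smaller.

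This is a minor improvement to a secondary aim. A reader might infer that the efficacy result is in doubt; it is not, since the Aim 1 analysis, sample size and test level do not depend on the mediation models.

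**What to change.** In the mediation text of the Data Analysis Approach:

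1. List the candidate mediators. Report the standardized indirect effect with its bootstrap interval for every one, whatever its size, from the single-mediator models already planned.
2. Fit one multiple-mediator model without selection on a small pre-specified set, for example one measure each for motivation, agency and stress/negative affect.
3. If backward selection is kept, state the retention rule, call the result exploratory, and repeat the selection inside every bootstrap resample.
4. Compare time points by their indirect effects and intervals. Report the proportion mediated as a description only.

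The cost is a few sentences and a small change of code. The downsides are wider intervals and a multiple-mediator model that must stay small because abstainers are few. Multiplicity also remains: with nine candidates, the chance that some null mediator's interval excludes zero is 0.19–0.25 without selection, against 0.28–0.32 with it. The existing caveat on type 1 error should therefore stay.
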